**Table 4 Schedule of Study Procedures and Assessments (ARM B)**

Study Day/Visit Day	Screening Day -28 to 0	Day 1	Day 22 (± 3 days)	Day 43 f (± 7 days)	Early Termination e	9 wks post RP (± 7 days)		6 months post RP (± 7 days)	12 months post RP (± 7 days)
Informed consent	X								
Baseline conditions	X								
AE assessment		X	X	X	RP	X	X	X	X
Concomitant medications	X	X	X	X		X	X	X	X
Obtain diagnostic biopsy or prostatectomy tissue	X				X				
Treatment/Drug Administration									
IPILIMUMAB		X	X		RP				
Clinical procedures									
Physical exam	X	X	X	X	RP	X	X	X	X
Vital signs d	X	X	X	X		X	X	X	X
Medical history	X								
Disease assessment	X							X	X
Performance status	X	X a	X	X		X	X	X	X
IPSS	X			X					
ECG	X								
Laboratory procedures									
CBC w/ Diff b	X	X a	X	X	RP	X	X	X	X
Blood chemistry b	X	X a	X	X		X	X	X	X
Thyroid Function Tests	X		X	X					
PSA	X			X		X	X	X	X
Hepatitis B, C and HIV	X								
Urinalysis	X								
HLA Typing	X								
Immune Monitoring c	X		X	X		X	X	X	X

a Pre-study clinical (physical exam and performance status) and laboratory parameters are to be measured within 14 days of beginning treatment and do not need to be repeated on Day 1.

b CBC with differential and platelet count will be collected prior to ipilimumab dose. Blood chemistry assessment, including: Alkaline phosphatase, ALT/AST, total bilirubin, calcium, phosphorus, BUN, creatinine, total protein, albumin, fasting glucose, potassium, sodium, chloride, LDH, carbon dioxide, lipase, amylase

c Refer to Laboratory Manual for collection procedures.

- d Vitals that are to be taken at screening and at every provider visit prior to ipilimumab administration are Blood pressure (diastolic & systolic), Heart Rate, Temperature, Respiration, & Pulse Oximetry. Weight is to be measured at screening and prior to Ipilimumab administration. Height is only required at screening. See section 6.1.3 for Vitals schedule before Ipilimumab administration.
- e Early termination visits are to be completed within 7 days for subjects who do not proceed to Radical Prostatectomy.
- f Subjects will have routine postoperative follow-up assessments 10-42 days following RP as per urologic oncologist's discretion. Concomitant medications, adverse events, and ECOG performance status should be evaluated.

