##### **4.4.1 Investigational Drug #3: Ipilimumab (Yervoy®, BMS)**

Ipilimumab is available as a sterile solution in the vial is clear and colorless. Ipilimumab is administered via intravenous infusion only.

Patients will receive ipilimumab 3 mg/kg IV administered over 90 minutes every 3 weeks for 2 doses (Arm B: Days 1 and 22; Arm C: Days 15 and 36). Vital signs, including blood pressure, heart rate, respiratory rate, temperature and pulse oximetry, will be monitored before ipilimumab infusion.

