### **5.6.3 Management of Hepatotoxicity**

Liver function tests (AST, ALT, T. bilirubin) will be evaluated for every subject prior to administration of ipilimumab. Blood samples must be collected and analyzed at local or central labs within 3 days prior to dosing. LFT results must be reviewed by the principal investigator (or designee) to meet dosing criteria specifications:  $\leq 2.5 \times \text{ULN}$  for AST, ALT and  $\leq 1.5 \times \text{ULN}$  for T. bilirubin unless liver metastases are present in which case LFT  $\leq 5 \times \text{ULN}$  for AST, ALT and T. bilirubin  $\leq 3.0 \times \text{ULN}$  prior to dosing.

If, during the course of treatment abnormal LFT values are detected, the subject must be managed using the hepatotoxicity algorithm section in the appendix 7.

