### **6.1.1.2 Screening Assessments (ALL ARMS)**

Subject screening evaluations must be performed within 28 days prior to enrollment; however, informed consent may be obtained earlier. Written informed consent will be obtained prior to the conduct of any study related procedures. At screening, the subject's name will be entered onto a screening log and a unique subject number will be assigned.

The subject's medical history and demographic information will be reviewed and recorded. The subject's PSA values following prostate cancer diagnosis will be collected and recorded on a eCRF. Each subject will undergo a comprehensive physical examination, including collection of vital signs, performed by the Investigator. The subject's ECOG performance status and American Urological Association (AUA) symptom index will be determined (See Appendix 1 and Appendix 4, respectively).

After eligibility is confirmed, the subject will be enrolled within 1 week prior to the first scheduled administration of study treatment.

The Screening procedures and assessments must be completed within 28 days of first day of infusion (**Week 1 Day 1**).

- Physical examination
- Vital signs including blood pressure, heart rate, respiratory rate, temperature, pulse oximetry, height, weight
- Complete medical history
- Baseline conditions assessment
- Documentation of disease assessment
- ECOG Performance status and International Prostate Symptom Score (IPSS)
- Baseline medications taken within 28 days of Day 1
- Obtain diagnostic biopsy
- Complete blood count (CBC) with differential and platelet count
- Blood chemistry assessment, including: Alkaline phosphatase, aspartate aminotransferase/alanine aminotransferase (ALT/AST), total bilirubin, calcium, phosphorus, blood urea nitrogen (BUN), creatinine, total protein, albumin, fasting glucose, potassium, sodium, chloride, lactate dehydrogenase (LDH), carbon dioxide, Lipase, Amylase
- TSH and T4
- PSA
- Immune monitoring

- HLA typing
- Serum Hepatitis assessment, including Hepatitis B surface antigen (HBsAg), Hepatitis B surface antibody (HBsAb), Hepatitis B core antibody (HBcAb), Hepatitis C virus RNA
- Urinalysis
- ECG

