#### **6.1.2.2 Study Procedures: ARMS A&C, Day 15:**

- Before administration of study drug:
  - Physical Exam
  - Vital signs including blood pressure, heart rate, respiratory rate, temperature, pulse oximetry, weight
  - ECOG PS
  - Evaluation of adverse events
  - Concomitant medications
  - CBC with differential and platelet count
  - Blood chemistry assessment, including: Alkaline phosphatase, ALT/AST, total bilirubin, calcium, phosphorus, BUN, creatinine, total protein, albumin, fasting glucose, potassium, sodium, chloride, LDH, carbon dioxide, lipase, amylase
  - TSH and T4
  - Immune monitoring

- Study drug administration
  - Arms A&C: Dosing of PROSTVAC-F subcutaneously in the left thigh
    - Vital signs including blood pressure, heart rate, respiratory rate, temperature, pulse oximetry, and weight will be taken within 30 min before dosing of PROSTVAC-F.
  - Arm C: Dosing of Ipilimumab
- Following administration of both PROSTVAC-F and Ipilimumab:
  - Vital signs including blood pressure, heart rate, respiratory rate, temperature, pulse oximetry, and weight will be taken within 30 min after dosing.
  - Observation for adverse events for 30 minutes in the clinic after each drug administration.

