#### **6.1.3.2 Study Procedures: ARM B, Day 22:**

- Before administration of study drug:
  - Physical Exam
  - Vital signs including blood pressure, heart rate, respiratory rate, temperature, pulse oximetry, weight
  - ECOG PS
  - Evaluation of adverse events
  - Concomitant medications
  - CBC with differential and platelet count
  - Blood chemistry assessment, including: Alkaline phosphatase, ALT/AST, total bilirubin, calcium, phosphorus, BUN, creatinine, total protein, albumin, fasting glucose, potassium, sodium, chloride, LDH, carbon dioxide, lipase, amylase
  - TSH and T4
  - Immune monitoring
- Before dosing of Ipilimumab
  - Vital signs including blood pressure, heart rate, respiratory rate, temperature, pulse oximetry within 30 min of dosing.
- Dosing of Ipilimumab

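### Table 4 lets the liver tests for Arm B's first ipilimumab dose be up to 14 days old, while section 5.6.3 requires them within 3 days of dosing

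*Combined protocol and SAP*

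**What the plan says.** **Liver tests before ipilimumab.** Section 5.6.3 states: "Liver function tests (AST, ALT, T. bilirubin) will be evaluated for every subject prior to administration of ipilimumab". It continues: "Blood samples must be collected and analyzed at local or central labs within 3 days prior to dosing". The results are then reviewed against stated dosing limits.

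**Arm B schedule.** Section 4.4.1 gives the ipilimumab days as "Arm B: Days 1 and 22; Arm C: Days 15 and 36". Table 4 marks the Day 1 blood count and chemistry with footnote a, under which "laboratory parameters are to be measured within 14 days of beginning treatment and do not need to be repeated on Day 1". Footnote b defines the panel: "Blood chemistry assessment, including: Alkaline phosphatase, ALT/AST, total bilirubin, calcium, phosphorus, BUN, creatinine" and further items. Section 6.1.3.1, the visit text for the same day, lists the count and the chemistry before dosing and mentions no waiver.

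**Arms A and C.** Table 3 carries the same footnote a on Day 1, when the only product given is PROSTVAC-V.

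**Checks after the infusion.** For Arm C, sections 6.1.2.2 and 6.1.2.3 schedule vital signs within 30 minutes after dosing and "Observation for adverse events for 30 minutes in the clinic after each drug administration". For Arm B, the lists in 6.1.3.1 and 6.1.3.2 place vital signs before the infusion (Day 22: "Vital signs including blood pressure, heart rate, respiratory rate, temperature, pulse oximetry within 30 min of dosing", under a pre-dose item) and stop at the dosing step. Footnote d of Table 3 points to a vital-sign schedule on both sides of dosing. Footnote d of Table 4 points only to one before dosing.

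**The concern.** Section 5.6.3 makes a recent liver result a condition for giving ipilimumab. Footnote a appears to have been written once and used in both schedules. In Table 3 it does not touch ipilimumab, because Day 1 is a vaccine dose. In Table 4 the same words fall on an ipilimumab dose and allow an older sample than 5.6.3 does. Section 6.1 directs sites to Tables 3 and 4 for the required tests, and no order of precedence between table and text is given. A coordinator working from Table 4 could therefore act in good faith and still depart from a mandatory pre-dose safety check, in one arm only.

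The post-infusion difference matters less and in another way. Arms B and C receive the same ipilimumab dose, and adverse events are tabulated by treatment group (section 8.7). If acute reactions are looked for on a schedule in one arm and not in the other, part of any difference in those tables could come from how closely patients were watched.

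**Working it through.** The protocol states no figure to reproduce here. The check sets the sections side by side.

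**Step 1. Do the two rules cover the same tests?** Section 5.6.3 names AST, ALT and total bilirubin. The Table 4 chemistry panel (footnote b) contains all three. The rules overlap on these tests and no others: 5.6.3 sets no 3-day limit for the blood count or the remaining chemistries.

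**Step 2. At which ipilimumab doses does the waiver apply?**

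| Ipilimumab dose | Chemistry entry in the schedule | Footnote a applies? |
|---|---|---|
| Arm B, Day 1 | Table 4, marked a | Yes |
| Arm B, Day 22 | Table 4, unmarked | No |
| Arm C, Day 15 | Table 3, unmarked | No |
| Arm C, Day 36 | Table 3, unmarked | No |

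Only the first Arm B dose is affected. Arm A receives no ipilimumab.

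**Step 3. How far apart are the rules?**

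- Oldest sample accepted by footnote a: 14 days.
- Oldest sample accepted by 5.6.3: 3 days.
- Difference: 14 − 3 = 11 days.

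Samples 0 to 3 days old satisfy both rules. Samples 4 to 14 days old satisfy footnote a and breach 5.6.3.

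**Step 4. How many doses are exposed?** The abstract plans 14 men per arm. Each Arm B man has two infusions, so the arm has 14 × 2 = 28, of which the 14 on Day 1 are exposed, or 14/28 = 50%. This is the number open to the conflict and not a forecast of breaches.

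**Step 5. Does 6.1.3.1 settle it?** A site following that visit text would draw the panel on Day 1. But footnote a says expressly that no repeat is needed, so the text and the table disagree with each other as well.

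**Step 6. Scheduled checks after ipilimumab.** Arm C also has 14 × 2 = 28 planned infusions. Vital signs and observation after dosing are scheduled for 28 of 28 in Arm C and for 0 of 28 in Arm B. Sections 4.4.1 and 5.1 do not fill the gap: 4.4.1 mentions vital signs before the infusion, and the 30-minute observation in 5.1 is written for the PROSTVAC injections.

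**The case against.** The best defence is that footnote a permits and 5.6.3 commands. A site can satisfy both by sampling within 3 days, and 6.1.3.1 leads it to do so. This stands to the extent that a breach is possible and not inevitable. A reader might infer that following Table 4 necessarily breaks 5.6.3, and the documents do not support that.

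The clinical exposure is also limited. The dose concerned precedes any study drug. Entry limits in section 3.3.1 are 1.5 times the upper limit of normal for AST, ALT and bilirubin, while the 5.6.3 dosing limits without liver metastases are 2.5 times for AST and ALT and 1.5 times for bilirubin. A man eligible on his screening sample therefore already met every dosing limit on that sample. This lowers the stakes, but it does not supply the recent sample that 5.6.3 demands, and for bilirubin the two limits coincide.

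Other stronger readings are tempting and fail:

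- *The Arm B liver baseline is missing.* It is not. Screening chemistry is required in all arms, and under footnote a the baseline may be up to 14 days old.
- *The screening window is a third conflicting rule.* Section 6.1.1.2 says "The Screening procedures and assessments must be completed within 28 days of first day of infusion". That is an outer limit for all screening items, and a 14-day laboratory limit fits inside it.
- *The arm-stopping rule is compromised.* Section 5.1.1 compares each arm with a fixed criterion for Grade 3 or higher events. Nothing shows that the absence of a scheduled 30-minute check would hide such an event.

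On post-infusion checks, the Arm B text is consistent with itself across 4.4.1, 5.1, 6.1.3 and Table 4, and Arm C men receive a vaccine on the same day, which may explain the difference. Section 5.6.2 covers symptomatic reactions in any ipilimumab patient, and section 8.7 plans no testing of adverse events. These arguments make the point secondary. They do not remove the asymmetry, because the Arm C observation follows each drug, ipilimumab included.

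**Conclusion.** The contradiction holds for one set of tests at one dose. For AST, ALT and total bilirubin before Arm B's Day 1 ipilimumab, Table 4 accepts results up to 14 days old and section 5.6.3 accepts at most 3, while section 6.1.3.1 lists the tests with no waiver. Up to 14 first doses could be given on results that satisfy the table and breach 5.6.3. This count assumes the planned 14 men in Arm B, all treated. How many doses would actually be affected depends on site practice, which the protocol does not show.

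The difference in scheduled post-infusion checks is real but secondary. It bears on how descriptive by-arm tables of acute infusion reactions are read. It does not touch the primary endpoint, and a reader who infers that Arm B monitoring is wrong goes further than the documents allow.

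**What to change.** 1. Reconcile Table 4 footnote a, section 5.6.3 and section 6.1.3.1 so that a single look-back governs the liver tests that release the Arm B Day 1 dose. Which interval applies is for the sponsor to decide.
2. Word footnote a separately for Table 3, where Day 1 is a vaccine dose, and Table 4, where it is an ipilimumab dose.
3. Reconcile the post-dose lists in 6.1.2.2 and 6.1.2.3 with those in 6.1.3.1 and 6.1.3.2, together with footnote d of the two tables. Otherwise, state that the difference is intended and note in section 8.7 that acute infusion reactions are ascertained unequally in Arms B and C.

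The cost is a wording change. Depending on the interval chosen, it adds either nothing or at most one routine blood draw for those Arm B men whose screening sample falls outside it. Item 3 needs no new procedure if the sponsor confirms that the difference is intended.

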## 6.2 Usage of Concurrent/Concomitant Medications

Concomitant medications associated with RP will not be recorded on the concomitant medication eCRF unless the need for the medication is judged to be at least possibly related to treatment with PROSTVAC or ipilimumab or may be immunosuppressive. Concomitant medications that are considered by the Investigator to be related to RP will be documented in the source documentation but will not be recorded on an eCRF

## 6.3 Dietary Restrictions

No dietary restrictions to this protocol.

## 6.4 Prohibited Medications

The following should not be used at any time during the study:

- Any investigational product other than PROSTVAC or Ipilimumab;
- Corticosteroid administration (inhaled, intra-articular and topical steroids are allowable)
- Vaccine therapy

Additionally, patients in this study may not use vaccines for or prevention of disease (including those for common medical conditions, e.g. influenza) while they are participating in this clinical study, and for 3 months following the final study treatment.

## 6.5 Restricted Medications

Hormones, including LHRH agonists, antiandrogens (such as bicalutamide, flutamide, or nilutamide), or 5- $\alpha$ -reductase inhibitors may not be administered until after RP. Additionally, radiation therapy may not be initiated until after RP. Following RP, subjects may receive hormone therapy or radiation therapy as deemed appropriate by their medical professional. Systemic anti-cancer therapies not listed above should be discussed with the medical monitor prior to initiating treatment.

# 7 Reporting and Documentation of Results

## 7.1 Evaluation of Activity

### 7.1.1 Primary endpoint: Immunohistological Characterization of CD3+ T Cell Infiltration within Prostate Tissue.

The primary endpoint response measure will be the change in the number of infiltrating CD3+ T cells/ $\mu\text{m}^2$  within the prostatic tumor tissue from the diagnostic core biopsy specimens to the post-treatment prostatectomy tissue specimens, based upon IHC analysis. The infiltrate will be scored by the number of CD3+ cells/ $\mu\text{m}^2$ . Thus, the number of inflammatory cells will be normalized to the unit area. Both biopsies and RP specimens will be quantitated with this frequency. For each patient, the change in the number of CD3+ T-cell infiltration from the pre-treatment biopsy to post-treatment prostatectomy tissue specimens will be represented by the ratio of post-treatment prostatectomy tissue specimens vs. pre-treatment biopsy.

### 7.1.2 Secondary and exploratory endpoints.

#### 7.1.2.1 Immunohistological characterization of T Cell Subsets and other Immune Cells within the Prostate Tissue.

The change in the number of infiltrating T cells/ $\mu\text{m}^2$  of selected subsets (e.g., CD4+, CD8+) within the prostatic tumor tissue from the diagnostic core biopsy specimens to the post treatment prostatectomy tissue specimens will be assessed, based upon IHC analysis.

#### 7.1.2.2 Antigen-specific T Cell Immunity in Peripheral Blood

To assess antigen-specific T cell immunity in the peripheral blood, indicated by the T cell response to PSA-3, peripheral blood samples will be collected from subjects at the screening visit, prior to RP and at 9 weeks post-RP. The frequency of PSA, TAA and vector specific T cells will be enumerated by interferon gamma (IFN- $\gamma$ ) enzyme-linked immunospot (ELISPOT) assays using established methods (41).

T-cell proliferation assay will also be measured at the same timepoints the antigen-specific T cell response by co-culturing previously cryopreserved PBMCs in triplicate with PSA, TAA, viral vector or PHA-L, and assessing with a standardized [ $^3\text{H}$ ] thymidine proliferation assay (48),(49).

### 7.1.3 PSA

The utility of a decline in PSA as a marker of response to neoadjuvant therapies is not well defined. However, the proportion of patients with PSA response, defined as  $\geq 50\%$  PSA decline, will be reported.

### 7.1.4 Pathologic Response

The proportion of patients with pathologic complete response (pT0) at the time of prostatectomy will be reported.

## 7.2 Evaluation of Safety

The following will be collected to evaluate safety:

- Adverse events (including SAEs and deaths)
- Physical examinations
- Vital signs
- ECOG performance status
- AUA symptom index
- Laboratory test results

Analyses will be performed for all patients having received at least one dose of study drug. The study will use the CTCAE v4.03 for reporting of non-hematologic adverse events and modified criteria for hematologic adverse events.

*For multicenter studies, the Principal Investigator at the UCSF Coordinating Center will hold the role of Study Chair. The Study Chair is responsible for the overall conduct of the study and for monitoring its safety and progress at all participating site.*

## 7.3 Definitions of Adverse Events

### 7.3.1 Adverse event

An adverse event (also known as an adverse experience) is defined as any untoward medical occurrence associated with the use of a drug in humans, whether or not considered drug related. More specifically, an adverse event can be any unfavorable and unintended sign (e.g., an abnormal laboratory finding), symptom, or disease temporally associated with the use of a drug, without any judgment about causality. An adverse event can arise from any use of the drug (e.g., off-label use, use in combination with another drug) and from any route of administration, formulation, or dose, including an overdose.

### 7.3.2 Adverse reaction

An adverse reaction is defined as any adverse event caused by the use of a drug. Adverse reactions are a subset of all suspected adverse reactions for which there is reason to conclude that the drug caused the event.

#### 7.3.2.1 Suspected

A suspected adverse reaction is defined as any adverse event for which there is a reasonable possibility that the drug caused the adverse event. For the purposes of IND safety reporting, "reasonable possibility" indicates that there is evidence to suggest a causal relationship between the drug and the adverse event. A suspected adverse reaction implies a lesser degree of certainty about causality than an adverse reaction.

#### 7.3.2.2 Unexpected

An adverse event or suspected adverse reaction is considered *unexpected* if it is not listed in the investigator brochure or package insert(s), or is not listed at the specificity or severity that has been observed, or, if an investigator brochure is not required or available, is not consistent with the risk information described in the general investigational plan or elsewhere in the current application.

"Unexpected," as used in this definition, also refers to adverse events or suspected adverse reactions that are mentioned in the investigator brochure as occurring with a class of drugs or as anticipated from the pharmacological properties of the drug, but are not specifically mentioned as occurring with the particular drug under investigation.

Adverse events that would be anticipated to occur as part of the disease process are considered *unexpected* for the purposes of reporting because they would not be listed in the investigator brochure. For example, a certain number of non-acute deaths in a cancer trial would be anticipated as an outcome of the underlying disease, but such deaths would generally not be listed as a suspected adverse reaction in the investigator brochure.

Some adverse events are listed in the Investigator Brochure as occurring with the same class of drugs, or as anticipated from the pharmacological properties of the drug, even though they have not been observed with the drug under investigation. Such events would be considered *unexpected* until they have been observed with the drug under investigation. For example, although angioedema is anticipated to occur in some patients exposed to drugs in the ACE inhibitor class and angioedema would be described in the investigator brochure as a class effect, the first case of angioedema observed with the drug under investigation should be considered *unexpected* for reporting purposes.

